1.4 Overall Rationale for the Study

Visterra is developing VIS410, a fully human IgG1 antibody, as a broad spectrum therapeutic agent against all strains of influenza A virus. New alternative treatments for influenza are urgently needed. Severe influenza disease occurs seasonally in many high-risk groups, such as young children, older adults, patients with pulmonary conditions, inflammatory conditions, malignancies, and pregnant women.^{1,2} Current influenza therapies are limited to the neuraminidase inhibitors, including oseltamivir (Tamiflu), zanamivir (Relenza) and peramivir (Rapivab). In spite of these available treatments, 10% to 44% of hospitalized patients require intensive care, and 25% to 50% of these patients die. In the United States, it is estimated that as many as 400,000 patients are hospitalized with influenza each year, with up to 49,000 deaths per year.³ A comparison of annual mortality rates from infectious disease in the United States further demonstrates the lack of effective interventions against this deadly disease (Table 5).

Table 5. Annual Mortality Rates from Infectious Diseases in the United States

Disease	Approximate No. of Deaths per Year
Influenza (varies by season)	25,000-49,000
Methicillin-resistant Staphylococcus aureus (2005)	18,650
Hepatitis C (2007)	15,000
Acquired immune deficiency syndrome (2007)	12,700
Invasive pneumococcal disease from Streptococcus pneumoniae (2009)	5,000
Hepatitis B	1,800

Furthermore, certain strains of influenza have comparatively high mortality rates: the 1918 H1N1 Spanish flu strain resulted in deaths of 1% to 3% of the world's population, compared with the 1968 pandemic strain that killed 0.03% of the world's population. In more recent years,

avian H5 and H7 strains have been documented to have 33% to 60% mortality rates despite the use of currently licensed antiviral treatments. Furthermore, the continued emergence of resistance to current antiviral drugs increases the need for new therapeutics.

This study will be used to determine the efficacy and safety of VIS410 in hospitalized subjects with influenza A infection requiring oxygen support, and is an important study for progression of the program toward evaluating VIS410 in severe influenza and those at high risk.

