10.6.3 Time to Clinical Response

Time to clinical response is defined as resolution of 4 of 5 vital signs that will be determined upon physical examination. Clinical response is defined as:

- Afebrile with core temperature $\leq 37.8^{\circ}\text{C}$, without use of antipyretics (oral $\leq 37.2^{\circ}\text{C}$)
- Respiratory rate ≤ 24 beats per minute
- Oxygen saturation $\geq 95\%$ on room air without support or a return to pre-infection status, if pre-infection status was $< 95\%$
- Pulse rate $\leq 100/\text{min}$
- SBP ≥ 90 mm/Hg, without vasopressor use

The probability of time to clinical response (defined as resolution of vital signs) will be calculated via Kaplan-Meier. A significance test (using the log-rank test) for each VIS410 dose vs placebo will be presented. The number and percentage of subjects in each treatment group with clinical response will be summarized. Results will be tabulated and presented graphically as well.

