## 2 STUDY DESIGN AND OBJECTIVES

### 2.1 Trial Design

This is a Phase 2b, multicenter, randomized, double-blind, controlled study comparing the efficacy and safety of 2 dose levels of VIS410 (2000 and 4000 mg) in combination with oseltamivir vs oseltamivir alone in hospitalized subjects with influenza A infection requiring oxygen support. Subjects will be randomly assigned at a ratio of 1:1:1 using a permuted block randomization method to receive VIS410 at a dose of 2000 mg (low dose) or 4000 mg (high dose) or placebo (0.9% sodium chloride), administered as a single IV infusion over 2 hours. Randomization will be stratified by presence or absence of positive pressure ventilation (PPV) at baseline to ensure an even distribution across treatment arms. All subjects will receive oseltamivir 75 mg twice daily (BID) for 5 days (total of 10 doses) as part of standard of care. Treatment with oseltamivir may be extended for up to 5 additional days (up to 20 doses of total therapy) if clinical symptoms warrant further treatment as assessed by the Investigator. Depending on standard of care, subjects may have started oseltamivir therapy prior to randomization. All subjects will also receive a pretreatment regimen of diphenhydramine 50 mg PO or IV plus either ibuprofen 400 mg PO or acetylsalicylic acid 320-325 mg PO approximately 60 minutes before infusion. Approximately 120 evaluable subjects (40/arm) with confirmed influenza A infection will be treated.

Study assessments are outlined in the Schedule of Assessments (copy in Appendix 16.2). Subjects discharged from the hospital prior to Day 14 will attend the applicable out subject follow-up visit(s) (e.g., Day 3, Day 5, Day 7, Day 14) per Table 1. The total study duration for each subject (screening through study exit) will be approximately 8 weeks (Day 56).

January 17, 2019

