## 2.2 Primary Hypothesis

The primary hypothesis for the study is that treatment with VIS410 + oseltamivir will lead to better clinical outcomes compared to oseltamivir alone.

The study is exploratory in nature and is not powered to demonstrate significant differences between treatment groups in primary or secondary outcome measures. The protocol intent is to collect sufficient information to identify the most appropriate candidate endpoints for subsequent Phase 3 study evaluation from among the primary and secondary endpoints described below. Statistical significance testing will therefore be used to assess the relative strength of evidence of the primary and secondary endpoints, to provide reasonable assurance that the endpoints chosen for a confirmatory Phase 3 trial will elucidate treatment differences between VIS410 plus oseltamivir versus oseltamivir alone.

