## 4 GENERAL ANALYSIS DEFINITION

### 4.1 General Considerations

All statistical analyses and summary information are to be generated according to this SAP. Any deviations from this SAP will be documented in the clinical study report (CSR).

These descriptive statistics will be presented for continuous parameters: the number of subjects used in the calculation (n), mean, standard deviation (SD), median, minimum, and maximum values. For PK parameters, the geometric mean and coefficient of variance (CV) will also be presented. All continuous summaries will display the minimum and maximum value with the same number of decimals collected in the data. The median, mean, geometric mean and CV will display 1 additional decimal, and the SD and SE will display 2 additional decimals. For categorical variables, frequencies and percentages will be reported. All percentages will be reported to 1 decimal; all p-values will be reported to 3 decimals.

All temperature measurements will be presented as degrees Celsius. Degrees in Fahrenheit will be converted with this formula:

$$T_C = (T_F - 32) * (5/9),$$

where  $T_C$  is a Celsius temperature and  $T_F$  is a Fahrenheit measurement.

Since this is a phase 2 study rigorous control over type 1 error will not be used; all statistical comparisons will be performed using 2-sided tests at the 0.05 significance level, unless specifically stated otherwise. All null hypotheses will be defined as no treatment difference. All p-values are presented for informational purposes only; there will not be any adjustments for multiple comparisons.

All analyses, summary tables, figures, and data listings will be generated with SAS version 9.4 or higher. Specialized PK software will be used for some PK analyses.

Baseline is defined as the latest non-missing measurement taken prior to study drug administration.

January 17, 2019

All summaries will be by actual visit, no visit windows for analysis will be defined. In general, summaries will be by treatment groups, and will include a combined VIS410 treatment group, in addition to the individual low dose (2000 mg) VIS410, high dose (4000 mg) VIS410, and Placebo treatment groups, unless specified differently. Summaries of disposition, other baseline data, and adverse events will also include an overall column.

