### 9.2.3 Time to Clinical Response

Time to clinical response (days) is defined as time to the finding of normality (as defined below) for 4 out of 5 vital signs that will be determined upon physical examination. Clinical response is defined as:

- Afebrile with core temperature  $\leq 37.8^{\circ}\text{C}$ , without use of antipyretics (oral  $\leq 37.2^{\circ}\text{C}$ )
- Respiratory rate  $\leq 24$  beats per minute
- Oxygen saturation  $\geq 95\%$  on room air without support or a return to pre-infection status, if pre-infection status was  $< 95\%$
- Pulse rate  $\leq 100/\text{min}$
- SBP  $\geq 90$  mm/Hg, without vasopressor use

For determination of time to clinical response, achievement of any of the criteria above will carry forward to missing data at subsequent visits. Subjects who do not experience clinical response will be censored at the last available vital sign visit date. Time to Clinical response will be analyzed using Kaplan-Meier techniques.

Pre-infection oxygen saturation data on room air status was not collected on the CRF. Therefore, prior to database lock, for any subject with persistent oxygen saturation on room air  $< 95\%$ , a query to the investigator will be sent to request historic oxygen saturation on room air data. If a baseline oxygen saturation on room air value collected during 6 months prior to enrollment is available, the information will be captured and recorded in a spreadsheet maintained by data management at POI. This spreadsheet will be reviewed, signed and locked prior to database lock. This information will be used to define pre-infection oxygen saturation on room air for the purposes of calculating time to clinical response. If there are no available medical record data and oxygen saturation remains below 95% on room air, the subject will be analyzed as not experiencing clinical response.

Note, the number of vital signs abnormalities (utilizing the above criteria) may range from 0 to 5 for subjects enrolled in the trial, although the expectation is that all subjects will have at least one abnormality. Therefore, this analysis will be conducted in two ways. First, the probability of time to clinical response (defined as the finding of at least 4 of 5 normal vital signs using the criteria above) will be calculated via Kaplan-Meier; under this analysis, some subjects will have met criteria for a clinical response at baseline. Time to clinical response will be calculated as Date of

January 17, 2019

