Event – Date of Day 1. If the event was not achieved then the value will be censored and calculated as Date of the last available assessment – Date of Day 1. P-values for each VIS410 dose versus placebo, VIS401 total versus placebo and for VIS410 4000 mg versus 2000 mg will be presented. The number and percentage of subjects in each treatment group with clinical response will be summarized. Results will be presented graphically as well.

This analysis will be repeated for subjects with >2 vital signs abnormalities at baseline, using the same analysis algorithm described above; under this analysis, no subject will meet criteria for clinical response at baseline.

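### Time to clinical response censors deaths at the last assessment, so one minus Kaplan-Meier overstates response by up to about the proportion who die before responding

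*SAP*

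**What the plan says.** SAP 9.2.3 sets the estimator, "Time to Clinical response will be analyzed using Kaplan-Meier techniques", and the censoring rule, "Subjects who do not experience clinical response will be censored at the last available vital sign visit date". It restates the rule when it defines the time variable: "If the event was not achieved then the value will be censored and calculated as Date of the last available assessment". Neither sentence mentions death. Subjects who die without responding are covered because all non-responders are. The repeat analysis in subjects with more than two abnormal vital signs at baseline uses the same algorithm.

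SAP 9.2.3 promises p-values without naming a test. Protocol 10.6.3 names it: "A significance test (using the log-rank test) for each VIS410 dose vs placebo will be presented". It gives no rule for death either, and the missing-data conventions in SAP 4.2 do not supply one. No competing-risk or death sensitivity analysis is planned for this endpoint.

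Elsewhere the SAP does deal with death. Section 9.1 gives it the worst ordinal score, carried forward for deaths before Day 7. Section 9.2.1 plans an ordinal AUC analysis that leaves death out. Section 9.2.7 evaluates mortality at Days 14, 28 and 56. Section 9.2.3 itself also reports the number and percentage of responders by arm.

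**The concern.** Kaplan-Meier treats a censored subject as having the same future as those who remain at risk. That can be defended for someone who withdraws alive. It fails for someone who dies, because response is then impossible. One minus Kaplan-Meier no longer estimates the proportion who recover.

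Two things are at stake. First, the response curves are too favourable in any arm with deaths before response. Second, an arm with more such deaths is not penalised for them in the test. The trial's stated purpose (SAP 2.2, Protocol 10.1) is to use significance tests to judge which endpoints to take into Phase 3, and the protocol synopsis wants estimates for powering later endpoints. A recovery endpoint that does not count death as failure could mislead on both.

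**Working it through.** The plan states no event count, effect size or power for this endpoint, so there is no figure to reproduce. The study "is not powered to demonstrate significant differences between treatment groups in primary or secondary outcome measures".

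**1. Inputs.** Arm size comes from SAP 2.1: "Approximately 120 evaluable subjects (40/arm) with confirmed influenza A infection will be treated". The test level comes from SAP 4.1: "all statistical comparisons will be performed using 2-sided tests at the 0.05 significance level". The only mortality figures are background ones in Protocol 1.4: "10% to 44% of hospitalized patients require intensive care, and 25% to 50% of these patients die". They multiply to 0.10 × 0.25 = 2.5% at the low end and 0.44 × 0.50 = 22% at the high end, or 1.0 to 8.8 deaths per 40. This is a range for illustration, not a planning value. The median time to response is not given; 5 days is assumed.

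**2. A small example.** Of 40 subjects, three respond on each of Days 2 to 13 (36 in all), and one dies without response on each of Days 3, 4, 5 and 6. With deaths censored under the SAP rule:

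| Day | One minus Kaplan-Meier | Actual proportion |
|---|---|---|
| 7 | 47.7% | 18/40 = 45.0% |
| 10 | 73.9% | 27/40 = 67.5% |
| 13 | 100% | 36/40 = 90.0% |

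On Day 13 only three subjects remain at risk and all respond, so the last factor is 1 − 3/3 = 0. The median is Day 8 either way.

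**3. General size.** Take a constant response hazard a = ln 2 / 5 = 0.1386 per day, and a death hazard b = a·m/(1 − m), so that a proportion m eventually dies before responding. The SAP rule estimates 1 − exp(−at). The actual probability of response by time t is (1 − m)·[1 − exp(−at/(1 − m))]. Setting this to 0.5 gives the actual median, (1 − m)/a × ln[(1 − m)/(0.5 − m)].

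| m | Day 14, SAP rule / actual | Day 28 | Day 56 | Median (days) |
|---|---|---|---|---|
| 2.5% | 85.6% / 84.2% | 97.9% / 95.7% | 100.0% / 97.5% | 5.0 / 5.1 |
| 10% | 85.6% / 79.6% | 97.9% / 88.8% | 100.0% / 90.0% | 5.0 / 5.3 |
| 22% | 85.6% / 71.5% | 97.9% / 77.5% | 100.0% / 78.0% | 5.0 / 5.8 |

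The SAP-rule column does not change with m. The excess approaches m by Day 56, while the median moves by less than a day.

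**4. The test.** Log-rank simulations used 40 per arm, 2,000 runs, two-sided 0.05 and the same 5-day median in both arms. Deaths were either censored at death or kept as non-responders to Day 56.

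| Scenario (VIS410 vs placebo deaths before response) | Censored at death: mean Z, VIS410 found worse | Kept at risk: mean Z, VIS410 found worse |
|---|---|---|
| 22% vs 2.5%, equal response hazards | −0.03, 3.1% | −1.64, 37.8% |
| 22% vs 2.5%, those who die could never have responded | −1.03, 18.7% | −2.27, 63.9% |
| 10% vs 10% | near 0 | near 0 |

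**5. Where to place the common censoring time.** The final visit is Day 56 ± 7, so a living subject can be assessed up to Day 63. Suppose 35 of 40 have responded, four deaths are censored at Day 56, and the last living non-responder responds on Day 60. One subject is then at risk, the factor is 1 − 1/1 = 0, and Kaplan-Meier returns to 100%. With the deaths held beyond Day 63, five are at risk and survival without response is 5/40 × 4/5 = 4/40, so response is 90%, which is correct.

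**The case against.** A good deal can be said for the plan. Clinical response is one of many secondary endpoints in an exploratory study, and SAP 4.1 calls the p-values informational. The log-rank test with deaths censored is a legitimate comparison of response rates among subjects alive and not yet responding. The 2.5% to 22% range describes hospitalised influenza in general, whereas this trial excludes subjects likely to die within 48 hours or on extracorporeal oxygenation. Only deaths before response matter. Four of five normal vital signs suffice, and SAP 9.2.3 expects some subjects to meet that at baseline; those subjects are events and cannot be censored at death.

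A reader might infer that deaths disappear from the report, or that the log-rank test uses only survivors. The documents support neither. The crude percentages in 9.2.3 would show, for example, 36/40 = 90% against 32/40 = 80% if every survivor responded and the arms had 4 and 8 such deaths. Mortality is tabulated under 9.2.7. Subjects who die also count in the risk set until their last assessment.

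These points limit the size of the problem without removing it. Separate tables let a reader notice a discrepancy; they leave the curve, the median and the p-value as they were.

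**Conclusion.** The concern holds. Followed exactly, SAP 9.2.3 makes one minus Kaplan-Meier overstate the probability of response by up to roughly the proportion who die before responding. With 10% such deaths the excess is 6.1 points at Day 14 and 9.1 at Day 28. The median is little affected. The between-arm comparison ignores death as a failure to recover; the test is essentially unaffected when mortality is equal and can miss a disadvantage when it is not.

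The figures rest on an assumed 5-day median, constant hazards and assumed mortality. The 22% against 2.5% split is an extreme illustration. It would go too far to conclude that the endpoint comparison is invalid whatever the mortality, or that the primary analysis is affected: SAP 9.1 scores death explicitly there. This should be changed, but it does not undermine the trial.

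**What to change.** In SAP 9.2.3, keep subjects who die without prior response in the risk set as non-responders, censored at one common time after Day 63. Alternatively, treat death as a competing event, using cumulative incidence with Gray's test. The two give the same curve when no living subject is censored early. Censor subjects who withdraw alive at their last assessment. Keep the present rule as a sensitivity analysis, and report deaths before the event by arm beside each curve.

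Handle death the same way in two other sections:

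- **9.2.4, ventilator support.** Non-events are censored at the last available ordinal assessment. The SAP should say whether a carried-forward death score counts as one, and place the common time beyond the last ordinal assessment.
- **9.2.2, oxygen support.** No censoring rule is stated, so one is needed for death and for withdrawal.

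The cost is one rule and a changed censoring date. No new data are needed, because SAP 9.2.7 already derives all-cause death from four case report forms. The downside is that response estimates become somewhat less favourable and the effect measure combines recovery with survival. Keeping the present analysis alongside lets readers separate the two.

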³ Single nasopharyngeal swab will be obtained from one nostril for influenza A rapid test. This screening test is not necessary if the subject has a prior influenza A positive test by Rapid Antigen Test or with another commercially available test including PCR, FIA, or ELISA within the prior 48 hours of screening.
⁴ Collect all medications taken, including over-the-counter, within 7 days prior to VIS410/placebo administration.
⁵ Randomization will be stratified by presence or absence of positive pressure ventilation (PPV) at baseline to ensure an even distribution across treatment arms.
⁶ Subject diary will be provided upon discharge from the hospital and will record daily oseltamivir dosing (as applicable) and will have a daily VAS for assessing resumption of usual activities until either the subject reports that all usual activities (prior to influenza onset) can be performed or Day 56, whichever comes first. In addition, the Influenza Patient Reported Outcomes (FluPRO) Questionnaire will be provided and completed daily up until Day 14 (if applicable).
⁷ Additional safety assessments may be performed outside of the defined protocol criteria, at the Investigator's discretion.
⁸ Single 12-lead ECG will be performed after a 5-minute rest in supine position.
⁹ To be repeated only if screening and baseline visits are more than 24 hours apart.

-
- ¹⁰ Vital signs should be measured after 5 minutes of rest in a supine position and include heart rate, respiratory rate, and blood pressure. During hospitalization, vital signs will be measured at the end of the infusion on Day 1 and then BID (preferably at the same time each day) up until Day 14 or discharge from the hospital if this occurs prior to Day 14.
- ¹¹ Baseline SpO₂ on room air to be documented, if available. Once randomized, SpO₂ to be measured using pulse oximetry 3 times daily (approximately every 8 hours) at approximately the same time each day until stable. Stable SpO₂ is defined as two consecutive SpO₂ values of > 92% on room air that are at least 8 hours apart.
- ¹² During hospitalization, body temperature will be recorded at the end of infusion on Day 1 then BID up until Day 14 or discharge from the hospital if discharge occurs prior to Day 14. In cases where obtaining oral temperature is not possible, core temperature will be obtained. While hospitalized, the maximum temperature should be recorded for each 12-hour interval (from 12 AM to 12 PM and from 12 PM to 12 AM).

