3.2 Secondary Endpoints

- Among patients requiring supplemental oxygen therapy at the time of enrollment with baseline room air oxygen saturation of $\leq 92\%$, time to cessation of oxygen (O_2) support resulting in stable oxygen saturation (SpO_2) by pulse oximetry. Stable SpO_2 is defined as two consecutive SpO_2 values of $> 92\%$ on room air that are at least 8 hours apart.
- For any patient requiring supplemental oxygen therapy at the time of enrollment (regardless of oxygen saturation), time to cessation of oxygen support.
- The difference between VIS410 + oseltamivir and oseltamivir alone treatment groups in the following endpoints:
 - Peak viral load, viral AUC, duration of viral shedding, and time to resolution of viral load from nasopharyngeal swabs by $TCID_{50}$ and qRT-PCR
 - Time to clinical response defined as resolution of at least 4 of 5 vital signs
 - Afebrile with core temperature $\leq 37.8^\circ C$, without use of antipyretics (oral $\leq 37.2^\circ C$)
 - Oxygen saturation $\geq 95\%$ on room air without support or a return to pre-infection status, if pre-infection status was $< 95\%$
 - Pulse rate $\leq 100/min$
 - Systolic blood pressure ≥ 90 mm/Hg, without vasopressor use
 - Respiratory rate ≤ 24 beats per minute

- Clinical status ordinal scale mean area under curve for Days 1-7 and Days 1-14, using linear numeric scores for the ordinal categories.
- Comparison of clinical status ordinal scale scores for selected individual days (ie, Days 3, 4, 5, and 6)
- Comparison of clinical status ordinal scale scores using modified ordinal scale criteria (ie, pooling of selected severity criteria scores)
- Comparison of discrete ordinal scale parameters, including days of ventilator support, days in intensive care, and duration of hospitalization
- Number of days to resumption of usual activities
- All-cause and attributable mortality rates at Day 14, 28, and 56
- Total number of days in hospital and/or intensive care unit (ICU) from admission to discharge and rate of rehospitalization due to influenza A relapse/complication
- The incidence, severity, and duration of signs and symptoms of influenza-like illness as assessed by the FluPRO Questionnaire (see Appendix 14.1)
- Analysis of time to alleviation of signs and symptoms of influenza in the subset of subjects able to complete the Influenza Patient Reported Outcomes (FluPRO) Questionnaire at baseline and post-dose by Kaplan Meier analysis

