6.3 Procedures for Sample and Data Collection

6.3.1 SpO₂ Oxygen Support

Baseline SpO₂ on room air to be documented, if available. Once randomized, SpO₂ will be measured using pulse oximetry 3 times per day (approximately every 8 hours) at approximately the same time each day until stable according to Table 1. Stable SpO₂ is defined as two consecutive SpO₂ values of > 92% on room air that are at least 8 hours apart.

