## 16.6 List of Proposed Tables, Figures, and Listings

### 16.6.1 Tables

Table	Title	Population
14.1.1.1	Subject Disposition	ITT
14.1.1.2	Subject Disposition	MITT
14.1.1.3	Subject Disposition by Region and Site	ITT
14.1.2.1	Summary of Protocol Deviations	ITT
14.1.3.1	Demographics and Baseline Characteristics	ITT
14.1.3.2	Demographics and Baseline Characteristics	MITT
14.1.4.1	Medical History	ITT
14.1.4.2	Medical History	MITT
14.1.5.1	Prior Medications	ITT
14.1.5.2	Prior Medications	MITT
14.1.6.1	Concomitant Medications	Safety
14.1.7.1	Treatment Exposure and Compliance	Safety
14.1.7.2	Treatment Exposure and Compliance	MITT
14.2.1.1.1	Summary of Clinical Outcome on Seven-Level Ordinal Scale through Day 14	MITT
14.2.1.1.2	Summary of Clinical Outcome on Five-Level Modified Ordinal Scale through Day 14	MITT
14.2.1.1.3	Summary of Clinical Outcome on Seven-Level Ordinal Scale through Day 14 Sensitivity Analysis	MITT
14.2.1.2	Summary of Area Under the Curve for Seven-Level Ordinal Scale	MITT
14.2.1.3	Summary of Area Under the Curve for Seven-Level Ordinal Scale Excluding Death Outcome	MITT
14.2.1.4	Summary of Area Under the Curve based on Modified Five-Level Ordinal Scale	MITT
14.2.1.5	Summary of Area Under the Curve for Seven-Level Ordinal Scale Sensitivity Analysis	MITT
14.2.1.6	Additional Assessments for Seven-Level Ordinal Scale	MITT
14.2.1.7	Additional Assessments for Seven-Level Ordinal Scale Sensitivity Analysis	MITT
14.2.1.8	Summary of Proportions of Best and Worst Cases for Seven-Level and Modified Five-Level Ordinal Scale	MITT
14.2.2.1	Time to Cessation of O2 Support	MITT
14.2.3.1.1	Kaplan-Meier Estimates of Time to Clinical Response (Resolution of Vital Signs)	MITT
14.2.3.1.2	Kaplan-Meier Estimates of Time to Clinical Response (Resolution of Vital Signs) in Subjects with > 2 Vital Sign Abnormalities at Baseline	MITT

14.2.3.1.3	Kaplan-Meier Estimates of Time to Complete Clinical Response (Resolution of Vital Signs)	MITT
14.2.3.1.4	Kaplan-Meier Estimates of Time to Complete Clinical Response (Resolution of Vital Signs) in Subjects with >2 Vital Sign Abnormalities at Baseline	MITT
14.2.4.1	Kaplan-Meier Estimates of Time to Cessation of Ventilator Support	MITT
14.2.5.1	Summary of Healthcare Resource Utilization Parameters	MITT
14.2.5.2	Summary of Visual Analogue Scale Scores	MITT
14.2.6.1.1	Descriptive Summary of FluPRO Domain Scores, Component Scores, and Total Score	MITT

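### SAP 9.2.3 defines clinical response as at least 4 of 5 normal vital signs, yet one sentence makes oxygen saturation mandatory for subjects with no saturation value on medical record

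*SAP*

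**What the plan says.** Time to clinical response is a secondary endpoint. Protocol 3.2 words it as "Time to clinical response defined as resolution of at least 4 of 5 vital signs". SAP 9.2.3 opens with normality for "4 out of 5 vital signs that will be determined upon physical examination" and later, when it sets out the Kaplan-Meier analysis, gives the event as "the finding of at least 4 of 5 normal vital signs using the criteria above". The five signs are temperature, respiratory rate, oxygen saturation, pulse and systolic blood pressure. The saturation criterion is 95% or more "on room air without support or a return to pre-infection status, if pre-infection status was" below 95%.

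Between those two statements, SAP 9.2.3 deals with the fact that pre-infection saturation was not collected on the CRF. Before database lock, investigators are queried about any subject whose room-air saturation is persistently under 95%. A value from the six months before enrollment, if found, defines the pre-infection level. If no medical-record data are available and "oxygen saturation remains below 95% on room air, the subject will be analyzed as not experiencing clinical response". Subjects without a response are censored at their last vital-sign visit. A criterion that has been achieved carries forward over later missing values.

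Two further places bear on this. Protocol 6.3.1 has SpO2 read three times daily "at approximately the same time each day until stable according to Table 1", where stable means two consecutive room-air values above 92% at least 8 hours apart. Protocol Table 1, footnote 10, says the continuing vital signs "include heart rate, respiratory rate, and blood pressure". SAP 16.6.1 lists Tables 14.2.3.1.3 and 14.2.3.1.4, whose titles begin "Kaplan-Meier Estimates of Time to Complete Clinical Response (Resolution of Vital Signs", but SAP 9.2.3 does not say what a complete response is.

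**The concern.** A four-of-five rule lets any single sign remain abnormal. The sentence on missing records takes that freedom away for one sign and one group of subjects. Its wording disposes of the subject, not of the saturation criterion, so a programmer who follows it literally will override the four-of-five count.

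Two things are then at stake. First, the same data can give two different results, depending on which sentence of SAP 9.2.3 is coded. Second, classification turns on whether an old chart reading exists, which is not an outcome and may vary by site. The endpoint gets responder percentages and p-values for four treatment comparisons, and both documents say that such results will help to choose Phase 3 endpoints.

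The data collection adds a smaller difficulty. The rule that ends required SpO2 readings uses 92%, while the response criterion uses 95%. A subject who is stable at 93% or 94% may have no later reading, so an unmet saturation criterion can reflect when measurement ended. This matters most for complete clinical response, if that requires all five signs.

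**Working it through.** The plan gives no event count, effect size or power for this endpoint, so there is no figure to reproduce. The check is one of logic, with one illustration.

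**1. Enumerate the patterns.** Five signs, each normal or abnormal, give 2^5 = 32 patterns.

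- Four-of-five rule: C(5,4) + C(5,5) = 5 + 1 = 6 responder patterns.
- Literal sentence, for a subject with no record: saturation must be normal, plus at least three of the other four, so C(4,3) + C(4,4) = 4 + 1 = 5 responder patterns.
- Difference: 6 − 5 = 1. The pattern that changes is saturation abnormal with temperature, respiratory rate, pulse and systolic pressure all normal.

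**2. Compare three subjects who differ only in the record.** Each stays at 93% on room air and has the other four signs normal.

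| Historic saturation | Saturation criterion | Signs normal | Four-of-five | Literal sentence |
|---|---|---|---|---|
| Below 95%, current value back at that level | met | 5 | responder | does not apply |
| 95% or more | not met | 4 | responder | does not apply |
| No record | not met | 4 | responder | non-responder, censored |

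The second and third subjects have the same course and the same count of normal signs. Only the chart differs.

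**3. Test the sentence against the rest of SAP 9.2.3.** Every subject needs oxygen support at entry (Protocol 5.2.1, criterion 4), so the saturation criterion, which requires room air without support, will usually be unmet at baseline. Yet the section expects some subjects to meet the response definition at baseline. Those subjects must come mainly from the pattern with the other four signs normal. If such a subject later stays below 95% with no record, the four-of-five rule gives an event at time zero and the literal sentence gives censoring at the last visit.

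**4. Illustration of scale.** The documents do not give the share affected. Assume 40 per arm, 95% responders under four-of-five, a hazard ratio of 1.5, two-sided alpha 0.05, and a share f of each arm that meets all three conditions (no record, persistently below 95%, other four signs normal). Events in a two-arm comparison are d = 2 × (0.95 × 40 − 40f), and by Schoenfeld's formula power = Φ(√(d/4) × ln 1.5 − 1.96).

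| f | Lost per arm | d | Responders per arm | Power |
|---|---|---|---|---|
| 0 | 0 | 76 | 95% | 42.4% |
| 5% | 2 | 72 | 90% | 40.5% |
| 10% | 4 | 68 | 85% | 38.7% |
| 20% | 8 | 60 | 75% | 34.8% |
| 30% | 12 | 52 | 65% | 30.9% |

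For example, at f = 10%: √(68/4) × 0.4055 − 1.96 = 1.672 − 1.96 = −0.288, and Φ(−0.288) = 0.387. Every input except the 40 per arm and the alpha is an assumption. The responder percentage moves one for one with f; power moves less.

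**The case against.** The best defence is that the sentence is loosely worded and no one intends to override the rule. It closes a paragraph that is only about establishing pre-infection saturation, the operative event definition comes after it, and the remark about baseline responders makes sense only if saturation is not compulsory. On that reading, the sentence means that the saturation criterion is unmet. This is plausible and may well be the intent. It does not settle the matter, because the text names the subject and the outcome, and nothing in the section limits it to one component or to complete response.

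The defence also rightly limits what can be claimed. A reader might infer four stronger things that the documents do not support:

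- *Saturation below 95% alone makes a subject a non-responder, so everyone who recovers to 93–94% is counted as never responding.* The sentence applies only when no record is available, after sites have been queried. Subjects with a historic value are outside it.
- *SpO2 measurement ends for good at stability.* What ends is the required three-times-daily reading. The Table 1 SpO2 row is marked in its last column, footnote 7 allows extra assessments, and SAP 9.2.2 mentions outpatients when it discusses room-air readings. Absence from footnote 10 proves little, since body temperature is not listed there either and has its own row. Later readings are not required, but they are not ruled out.
- *The rule works against VIS410 because faster weaning brings the stopping point sooner.* The rule is the same in all arms, and nothing shows that the speed of weaning changes whether the final readings are 93–94% or at least 95%.
- *The number affected can be had by applying an assumed share stabilising at 93–94% to all 120 subjects.* That leaves out the other two conditions. Anyone with a further abnormal sign is a non-responder under either reading.

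Finally, this is one secondary endpoint in a study that both documents describe as exploratory and not powered, with p-values that the SAP calls informational. That lowers the stakes, but the contradiction remains.

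**Conclusion.** The contradiction is real. As written, SAP 9.2.3 gives two incompatible classifications for one pattern, low saturation with the other four signs normal, when no historic value exists. It also makes response depend on chart availability. This conclusion rests on the text alone and needs no assumption.

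Its size is unknown. A subject is affected only if there is no record, room-air saturation stays below 95% and the other four signs are normal, and the documents give no rate for that combination. The illustration shows what assumed shares would do and is not an estimate. No direction of bias between arms is shown. The primary endpoint is not affected.

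The gap between the 92% stopping rule and the 95% criterion is a secondary limitation. Under four-of-five its effect is small, because the other four signs can still carry the response. For complete clinical response it could matter more, but that depends on a definition the SAP does not give.

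**What to change.** Before unblinding, replace the sentence in SAP 9.2.3 with: 'If no pre-infection value is available and room-air saturation stays under 95%, the oxygen saturation criterion is treated as not met; clinical response is still determined as at least 4 of 5 criteria.' If the sponsor did mean saturation to be mandatory for these subjects, the SAP should say so, give the reason, and reconcile it with Protocol 3.2 and 10.6.3.

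In the same revision, define complete clinical response for Tables 14.2.3.1.3 and 14.2.3.1.4 and the matching figures. Add a note to those tables that scheduled SpO2 readings are required only until two room-air values exceed 92%, so a subject stable at 93–94% may have no later reading to document 95% or more.

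The cost is one replaced sentence, one definition and one table note. No new data are needed. A change to the SpO2 schedule is not needed to resolve the contradiction and, with an SAP dated January 2019, may come too late to help.
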